8. ADVERSE EVENTS

8.1. Definitions

8.1.1. Adverse Event

An adverse event (AE) is defined as any untoward medical occurrence in a subject or clinical investigation subject administered a medicinal product and which does not necessarily have a causal relationship with this treatment. An AE can therefore be any unfavorable and unintended sign (including an abnormal laboratory finding), symptom or disease temporally associated with the use of a medicinal product, whether or not considered related to the medicinal product.

Planned hospital admissions and/or surgical operations for an illness or disease that existed before the subject was randomized in a clinical study are not to be considered AEs.

Adverse events or abnormal test findings will be followed until the event (or its sequelae) or the abnormal test finding resolves or stabilizes at a level acceptable to the Sponsor/investigator.

8.1.1.1. AE Severity

The severity of an AE will be assessed by the investigator. The investigator should ensure that any subject experiencing an AE receives appropriate medical support until the event resolves.

Adverse events will be graded on a 3-point scale and reported as indicated on the case report form. The intensity of an AE is defined as follows:

- 1 = Mild: Discomfort noticed, but no disruption to daily activity.
- 2 = Moderate: Discomfort sufficient to reduce or affect normal daily activity.
- 3 = Severe: Inability to work or perform normal daily activity.

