1.2.2. Clinical Studies

One ongoing Phase I study has been conducted to date (Study ALN-PCSSC-001). This was a randomized, single-blind, placebo-controlled, single-dose escalation and multiple-dose study of ALN-PCSSC administered SC to subjects with elevated LDL-C. The study was conducted in two phases: a single ascending dose (SAD) phase and a multiple dose (MD) phase. During the SAD phase, 24 subjects were assigned to either receive placebo or one of five doses of ALN-PCSSC ranging from 25 mg to 800 mg. Those who received doses of at least 100 mg saw their LDL-C drop at least 40%; at the 500 mg dose, LDL-C levels dropped as much as 78%. At 140 days after the treatment was given, subjects still had an average LDL-C reduction of about 40%.

In the MD phase, 45 subjects received multiple doses of either ALN-PCSSC (125mg weekly x4, 250 mg bi-weekly x2, 300 mg and 500 mg twice given 1 month apart) or placebo. These subjects had maximal LDL-C reductions of 80% and average LDL-C reductions of 50% to 60%. To date, the drug appears to be generally safe and well tolerated. One subject on statin comedication had elevated liver enzymes with alanine aminotransferase (ALT) >4x the upper limit of normal (ULN), which resolved on stopping the statin.

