10.4.4.1. Adverse Events

The Medical Dictionary for Regulatory Activities (MedDRA) dictionary will be used for coding AEs. An AE (classified as preferred term) occurring during the double-blind treatment period will be counted as a treatment emergent AE (TEAE) either if it is not present at baseline or if it is present at baseline but increased in severity during the treatment period.

The number (percentage) of subjects reporting TEAEs for each preferred term will be tabulated by system-organ class, by system-organ class and severity, and by system-organ class and relationship to study drug. If more than one event occurred with the same preferred term for the same subject, the subject will be counted only once for that preferred term using the most severe or related occurrence for the summary by severity, or relationship to study drug, respectively.

Incidences of injection site reactions will also be presented by dose group (see also [Section 8.1.4](#)). Time to first injection site reaction will be analyzed. The severity and duration of injection site reactions, as well as their signs and symptoms, will also be summarized.

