3.2. AE Severity

The severity of an AE will be assessed by the investigator. The investigator should ensure that any subject experiencing an AE receives appropriate medical support until the event resolves.

Adverse events will be graded on a 3-point scale and reported as indicated on the case report form. The intensity of an AE is defined as follows:

- 1 = Mild: Discomfort noticed, but no disruption to daily activity.
- 2 = Moderate: Discomfort sufficient to reduce or affect normal daily activity.
- 3 = Severe: Inability to work or perform normal daily activity.

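### Apart from injection site reactions, AEs are graded only by discomfort and daily activity, so read literally a symptom-free laboratory AE cannot exceed Mild, and its worsening from a recorded baseline event is not treatment-emergent

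*Protocol*

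**What the plan says.** Protocol 8.1.1 defines AEs broadly, as anything untoward linked in time to taking the product: "An AE can therefore be any unfavorable and unintended sign (including an abnormal laboratory finding), symptom or disease temporally associated". SAP 3.1 has the same definition.

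Protocol 8.1.1.1 gives the grading rule. "The severity of an AE will be assessed by the investigator", and there are three levels:

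- The lowest is given as "1 = Mild: Discomfort noticed, but no disruption to daily activity".
- The middle one, Moderate, requires that the discomfort interferes with what the subject usually does.
- The highest is given as "3 = Severe: Inability to work or perform normal daily activity".

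SAP 3.2 repeats the scale: "Adverse events will be graded on a 3-point scale and reported as indicated on the case report form". Neither document says how a finding without symptoms is to be graded. A second scale, CTCAE v4.0 grades I to V, is given in Protocol 8.1.4 and SAP 3.6, for injection site reactions only.

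The grade is used twice in Protocol 10.4.4.1 and SAP 5.4.5.1. TEAEs are tabulated by severity, taking each subject's most severe occurrence of a preferred term. An AE is treatment-emergent if it was absent at baseline, or "if it is present at baseline but increased in severity during the treatment period".

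Laboratory values are also analysed outside the AE tables (Protocol 10.4.4.2, SAP 5.4.5.2). Absolute and percent changes are summarized by group and visit. The incidence of potentially clinically significant (PCS) values is reported only for subjects who had none at baseline, and no thresholds are given. SAP Section 7 declares no departures from the protocol's analyses.

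**The concern.** The scale measures how an event feels and what it stops the subject doing. A rise in ALT, creatine phosphokinase or glucose often does neither, so for these events the grade carries no information about size. It nevertheless decides where they fall in the severity table and, for events present at baseline, whether they count as treatment-emergent.

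This matters in this trial for three reasons. The drug is designed to act in the liver (Protocol 1.2). Exclusion 9 removes active liver disease and unexplained, confirmed ALT or AST elevations above 2x ULN, so subjects with raised enzymes below that limit can enter. And SAP 5.4.4 says that the safety results, with efficacy, will help choose the Phase III dose, so AE tables by arm are part of that evidence. Protocol 1.2.2 reports one Phase I subject on a statin with ALT above 4x ULN, which resolved when the statin was stopped. That shows the kind of event the scale cannot size.

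**Working it through.** The plan states no figure on this point and no sample-size or power input bears on it. The check applies the grading rule to a symptom-free laboratory AE and carries the result through the TEAE rule.

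**Step 1: grade.** Severe needs inability to function, so it is not met. Moderate needs discomfort that affects activity, so it is not met. Mild needs discomfort to be noticed, so on strict wording it is not met either. The grade is Mild by elimination, or there is none. The size of the abnormality enters at no level.

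**Step 2: severity table.** Every symptom-free laboratory AE, new or not, lands in the lowest row or in no row. With the grade left to the investigator and about 60 centers planned (Protocol 3.1), sites may also resolve the gap differently.

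**Step 3: TEAE rule.** Three cases:

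| Case | Grade change | TEAE? |
|---|---|---|
| (a) Laboratory AE absent at baseline | not needed | Yes, at any grade |
| (b) Recorded as an event at baseline, same preferred term, worsens without symptoms | none | No |
| (c) Abnormal value at screening, not recorded as an event, later reported as an AE | not needed | Yes, treated as new |

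Only case (b) is lost. Case (c) matters because AE recording starts at randomization (Protocol 8.2 and Table 3), and the documents do not say whether a raised screening value is entered as a baseline event.

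**Step 4: illustration, with assumed values.** Take ALT at 1.9x ULN at baseline, below the 2x ULN limit in exclusion 9, rising without symptoms to just above 4x ULN, the level in the Phase I case. The value has risen by a factor of 4 / 1.9 = 2.1. If the baseline elevation was recorded as an event, the grade goes from Mild to Mild (or from none to none) and the event is not a TEAE. If it was not recorded, the later event is a TEAE, shown as Mild or ungraded.

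**Step 5: does the laboratory analysis pick this subject up?** The value enters the group change summaries in either case. For the PCS incidence the answer depends on a threshold that is not stated:

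- Threshold above 1.9x and up to 4x ULN: no PCS value at baseline, one on study, so the subject is counted.
- Threshold below 1.9x ULN: already PCS at baseline, so the subject is left out.

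**The case against.** The case against is substantial.

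- A reader might infer that the discomfort scale is the only AE severity scale in the trial. It is not: injection site reactions have CTCAE.
- A reader might infer that worsening laboratory AEs in general drop out of the TEAE counts. Only an event already recorded at baseline under the same preferred term can drop out; anything new counts at any grade.
- A reader might infer that the worsening disappears from the analysis. It does not. Changes are summarized for all subjects without regard to baseline status, and the data are listed (Protocol 10.3.3). Seriousness is judged separately from severity and includes medically significant events (Protocol 8.1.2), and the DMC reviews safety data every two months.
- A reader might take the Phase I ALT case as an established drug signal. The protocol does not call it one, and it resolved on stopping the statin.
- The ceiling at Mild is an inference. The grade is the investigator's, reported as the case report form indicates, and that form is not available here.

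All of this stands and sets the limits of the point, but it does not remove it. Group summaries do not show how many individuals worsened or by how much. The PCS incidence can omit the same subjects that the TEAE rule omits. SAE reporting does not supply a severity grade. If investigators depart from the written anchors to grade by size, the table mixes two undeclared rules.

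**Conclusion.** The concern holds in limited form. For AEs other than injection site reactions, the written scale cannot rank symptom-free laboratory events by size. Two descriptive outputs suffer: the TEAE-by-severity tables, for all such events, and the TEAE count, for those already recorded at baseline under the same term that worsen without symptoms. No hypothesis test or efficacy endpoint is touched.

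The number of subjects affected cannot be derived from the documents. The conclusion assumes that the anchors are applied as written and that the case report form adds no laboratory grading. The TEAE part further assumes that at least some baseline abnormalities are recorded as events. The documents do not support any claim that laboratory harm would go unseen. The change is still worth making, because the stated rule makes the grade uninformative for these events and the remedy is cheap.

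**What to change.** 1. **Protocol 8.1.1.1 and SAP 3.2:** state that the investigator grades AEs that are laboratory abnormalities by CTCAE v4.0 where a grade exists, with grades 1, 2 and 3 or higher reported as mild, moderate and severe, and uses the 3-point scale otherwise. The investigator remains the grader; programmed grades do not replace that assessment.
2. **Protocol 10.4.4.1 and SAP 5.4.5.1:** state that for these events a rise of at least one grade over baseline is an increase in severity.
3. **Protocol 10.4.4.2 and SAP 5.4.5.2:** add a baseline-to-worst shift table for laboratory values in all subjects, including those abnormal at baseline.

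The cost is about a sentence in each place and one more table. No new samples or visits are needed, because central laboratory values are already collected at each visit from randomization. The downside is that more laboratory AEs will be shown as moderate or severe. Because the documents reproduce CTCAE only for injection site reactions, the sponsor should check which laboratory parameters it grades before finalizing the wording.

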8.1.1.2. Study Drug Causality

The relationship of an AE to study treatment will be assessed with consideration to the following criteria:

- Temporal relationship to the initiation of study medication
- Response of the event to withdrawal of study medication
- AE profile of concomitant therapies
- Clinical circumstances during which the AE occurred
- Subject's clinical condition and medical history

Categorization of causality will be designated by the investigator as stated below:

- **Reasonable possibility** - There are facts (evidence) or arguments to suggest a causal relationship between the event and study drug

- **No reasonable possibility** – There are few to no facts (evidence) or arguments to suggest a causal relationship between the event and study drug

8.1.2. Serious Adverse Event

A serious adverse event (SAE) is any untoward medical occurrence that at any dose:

- Results in death
- Is life-threatening, ie, the subject was, in the opinion of the investigator, at immediate risk of death from the event as it occurred (it does not include an event that, had it occurred in a more severe form, might have caused death)
- Results in a significant, persistent or permanent change, impairment, damage or disruption in the subject's body function/structure, physical activities and/or quality of life
- Requires in-subject hospitalization or prolongs hospitalization
- Is a congenital anomaly/birth defect
- Is another medically significant event that, based upon appropriate medical judgment, may jeopardize the subject and may require medical or surgical intervention to prevent one of the outcomes listed above (eg, allergic bronchospasm requiring intensive treatment in an emergency department or home, blood dyscrasias or convulsions that do not result in hospitalization, or the development of drug dependency or drug abuse)

A distinction should be drawn between serious and severe AEs. Severity is an estimate or measure of the intensity of an AE, while the criteria for serious AEs are indications of adverse subject outcomes for regulatory reporting purposes. A severe AE need not necessarily be considered serious and a serious AE need not be considered severe. For example, nausea that persists for several hours may be considered severe nausea, but not an SAE. On the other hand, an MI that may be considered minor could also be an SAE if it prolonged hospitalization.

8.1.3. Medication errors

Medication error refers to any unintended error in the dosing and administration of the study product as per instructions in the protocol. Medication Errors generally fall into four categories as follows:

1. Wrong medication
2. Wrong dose (including dosing regimen, strength, form, concentration, amount);
3. Wrong route of administration;
4. Wrong subject (ie, not administered to the intended subject)

Medication Errors include occurrences of underdose of the study product(s).

Underdose: Unintentional administration of an insufficient quantity of study drug; ie, incomplete administration of study drug as drawn for injection.

8.1.4. Adverse Events of Special Interest (AESIs)

An adverse event of special interest (serious or nonserious) is one of scientific and medical concern specific to the Sponsor's product or program, which warrants ongoing monitoring and rapid communication by the investigator to the sponsor. The SAE/AESI form should be utilized for reporting the AESI even if a serious outcome may not apply.

In this study, injection site reactions including individual signs or symptoms at the injection site reported following study drug-administration will be collected as an AESI.

Signs or symptoms of injection site reaction will be evaluated by the Common Terminology Criteria for Adverse Events (CTCAE) criteria of Injection Site Reaction (General disorders and administration site conditions) to determine the event's grade (severity) (see Table 4).

TABLE 4: COMMON TERMINOLOGY CRITERIA FOR ADVERSE EVENTS (CTCAE) OF INJECTION SITE REACTION

Grade I:	Tenderness with or without associated symptoms (eg, warmth, erythema, itching)
Grade II:	Pain; lipodystrophy; edema; phlebitis
Grade III	Ulceration or necrosis; severe tissue damage; operative intervention indicated
Grade IV	Life-threatening consequences; urgent intervention indicated
Grade V	Death

Reference source: Common Terminology Criteria for Adverse Events (CTCAE), Version 4.0, Published 28 May 2009.

As indicated in [Section 6.4](#), if a local reaction around the injection site occurs, photographs should be obtained either by the investigator or another health care professional at first presentation and at each of the follow-up visits until the injection site reaction resolves.

8.1.5. Other Safety Related Information

A comprehensive term that encompasses safety information for which global regulations require collection, evaluation, and/or reporting to Regulatory Authorities. Other safety-related information includes, but is not limited to, reports of the following:

- Abnormal neurological examination, eg, peripheral sensory and motor evaluation, an assessment of gait, pain, position, strength and reflexes ([Appendix A](#))
- Potential anaphylactic reactions assessed by Sampson criteria ([Appendix B](#))
- Suspected transmission via a medicinal product of an infectious agent
- Drug interactions
- Occupational exposure

Report the occurrence of suspected transmission via a medicinal product of an infectious agent, drug interactions, or occupational exposure to the Sponsor's GPV department as per [Section 8.3](#), Procedure for Serious Adverse Event Reporting. Note: The Special Situations event does not need to be serious to be reported on the SAE/AESI Report form.

The occurrences of abnormal neurological examination and anaphylactic reaction must be recorded on the source documentation and eCRF, and if the events are serious must be reported to the Sponsor's GPV department using the SAE Report form.

8.2. Procedure for Non-Serious Adverse Event Recording

All nonserious AEs that occur during the designated study period from randomization up to EOS must be assessed and recorded on the source documents and electric case report forms (eCRFs), regardless of causal relationship to the study drug. Note: For subjects in whom LDL-C levels have not returned to >80% of baseline values by Day 210, AEs will continue to be assessed at additional monthly follow-up visits (Day 240, Day 270, Day 300, Day 330, and Day 360) until the final observation.

8.3. Procedure for Serious Adverse Event Reporting

NOTE: This procedure may need to be followed for reporting AESIs or Other Safety Related information as noted in [Section 8.1.5](#) and [Section 8.5](#).

All SAEs that occur during the designated study period (from randomization through the EOS visit) must be reported to the Sponsor's Global Pharmacovigilance Department (GPV) within 24 hours of awareness of the event using the provided study specific SAE/AESI Report Form. The completion and processing of the SAE/AESI Report Form should be per the instructions in the provided SAE/AESI Report Form completion guidelines. In addition to completing the SAE/AESI Report Form, each SAE/AESI must be entered on the appropriate page of the eCRF. Note: For subjects in whom LDL-C levels have not returned to >80% of baseline values by Day 210, SAEs will continue to be assessed at additional monthly follow-up visits (Day 240, Day 270, Day 300, Day 330, and Day 360) until the final observation.

When death occurs with an SAE, the cause of death must be reported as an SAE. "Fatal" will be reported as the outcome for these events.

The investigator must assess the causality for each SAE/AESI.

The Sponsor will contact the investigator, if necessary, to clarify any of the event information. The investigator should provide any follow-up information for the event to the Sponsor on an updated SAE/AESI report form as soon as it becomes available.

If the investigator is notified of a SAE/AESI that occurs post-study period, that he or she wishes to report to the Sponsor (eg, an event suspected to be causally related to study drug), the event should be reported through the process described above.

Where appropriate, if required by local regulations or procedures, the investigator should report these events to the Institutional Review Board (IRB)/Ethics Committee (EC) and/or national regulatory authority in addition to the Sponsor.

8.4. Procedure for Medication Error Reporting

Medication errors (with or without an associated AE) need to be recorded as medication errors in the eCRF as described in [Section 8.2](#).

Medication errors with an associated SAE need to be recorded as medication errors in the eCRF and reported to the Sponsor's GPV department as described in [Section 8.3](#).

A mis-dosing protocol deviation (refer to [Section 12.3](#)) would need to be reported as a medication error if it was an “unintended error” as defined in [Section 8.1.3](#).

8.5. Procedure For Reporting Adverse Events Of Special Interest (AESIs)

The AESI of Injection Site Reaction has been identified for the study product(s) in this protocol as per [Section 8.1.4](#). Nonserious AESIs should be reported to The Medicines Company (MDCO) GPV within 72 hours and serious AESIs should be reported to MDCO GPV within 24 hours. In both instances, the reporting procedure provided in [Section 8.3](#) should be followed. The SAE/AESI form should be utilized for reporting the AESI even if a serious outcome may not apply.

8.6. Procedure For Reporting Pregnancies/Lactation Exposure

Occurrences of pregnancy/lactation exposure in a study subject or study subject's partner should be reported within 24 hours using the Pregnancy/Lactation Exposure Reporting form. In cases where a pregnancy/lactation exposure occurs with a SAE, the SAE reporting form should be used to report the SAE/AESI and the Pregnancy Reporting form should be used to report the pregnancy. When a pregnancy occurs without any concurrent SAE, the Pregnancy Reporting form may be submitted alone. The pregnancy must be followed through to outcome of pregnancy. Any pregnancy discovered after consent to follow-up need to be reported.

9. DATA COLLECTION

An electronic data capture (EDC) system will be used for this trial. All users will be trained on the technical features of the EDC as well as the content of the eCRF by qualified personnel prior to gaining access to the EDC. A UserID/Password will be granted after training. This ID is not to be shared amongst the study staff. All users must have a unique account to enter or review data. The eCRF should be filled out by the site 3 days after each visit. It is not expected that the eCRF will serve as source for any data collected in this trial. If there is a reason for a site to do so, it must be approved by MDCO and documented in the site files.

Prior to the database being locked, the investigator or designee will review, approve, and sign/date each completed eCRF corresponding to the blinded pages and the appropriate unblinded designee will similarly address the unblinded section of the eCRF. This signature serves as attestation of the investigator's responsibility for ensuring that all data entered into the eCRF are complete, accurate, and authentic. After the end of the trial, a copy of the data will be provided to the site. This copy will contain the final data, an audit trail of activity on the data, and any queries and answers that were posted for data clarification.

